Sample size and power: Given an expected final sample size of 36 (assuming 10% attrition to reduce threats to validity)⁴⁹ with data completed at the 3 time points, we will be powered at 80% power and 5% level of significance to detect a large effect size (Cohen's f = 0.53) for changes from baseline.

The study team for this study will be comprised of the principal Investigators, study coordinators, and co investigators/research assistants. The coordinator and co-investigators will be responsible for the day-to-day operations of the study including recruitment and data collection management and analysis. The administrative site will be at Emory University, Nell Hodgson Woodruff School of Nursing. All team members have completed CITI training. Study-specific training for staff who will be obtaining data by interview.

[name] is the primary individual charged with identification and reporting of all adverse events (AE) and serious adverse events (SAE). [name] will provide systematic routine monitoring for the following central elements: protocol eligibility (direct source documentation of eligibility as defined in the protocol), appropriateness of consent documentation, and timeliness and accuracy of data. Monitoring reports will be conducted on a bi-weekly basis and as needed and will be reviewed at the weekly core team meeting of the investigator team.

All caregiver survey assessment data will be audited upon completion of the study. Each audit will consist of review and evaluation of 1) conformance with informed consent requirements; and 2) individual subject case review to detect low data quality (e.g., inconsistent responses on a data element that should be the same throughout the study period, such as age within 1 year). All data that impact on the interpretation of primary study endpoints will be verified with source documents. Investigator compliance with the protocol also will be evaluated. We will encourage a culture of transparency to encourage self-report of protocol breaches.

19. Provisions to Monitor the Data to Ensure the Safety of Participants

This study does not involve more than minimal risk to study participants and will not require a data safety monitoring board (DSMB). However, we will incorporate a data safety monitoring plan (DSMP)ongoing monitoring of this study will be conducted by the PI [name] and research team throughout the study to ensure the study is conducted according to the approved protocol. In addition, Emory University's IRB will conduct regular reviews of study protocols, changes in study protocols, and adherence to protocols in the field. The PI [name] is required to report any unexpected study-related adverse events to the Emory IRB and NIH. An independent safety monitor or a data and safety monitoring board will not be used.

Page 15 of 32 Version: 1_05/05/2023

Plans for Assuring Compliance with Requirements Regarding the Reporting of Adverse Events: The Principal Investigator is responsible for reporting serious adverse events to the Emory's IRB and NIH within 48 hours of the occurrence.

A serious adverse event is defined as one that: is fatal or life-threatening (i.e., results in an immediate risk of death); requires or prolongs hospitalization; results in persistent or significant disability; is a birth defect; or is an important medical event that when based upon appropriate medical judgment, may jeopardize the participant, and may require medical or surgical intervention to prevent one of the outcomes listed above. Serious adverse events are not expected to occur during this study.

If there are instances of severe distress observed during the interviews, we will provide the caregiver with a list of resources that the caregiver may use, such as counseling services or resources offered by Alzheimer's Association. In emergent circumstances, the we will make a referral to the local emergency room.

Plans for Assuring Data Accuracy and Protocol Compliance: Under the direction of PI [name], all data will be managed in a secure fashion. All of the data will be kept on a secure server. In all of the data files, data will be coded by identification number only. Participants' names will be separated from the data and kept on a secure server or in a locked file cabinet. Access to the secure server and the file cabinet will be strictly controlled by the Principal Investigator.

Data Maintenance: We will use REDCap to minimize data entry errors. All data entry screens are set up in REDCap and, where possible, include data delimiters (i.e., skip patterns, valid range limits) to ensure correctness and minimize missing data.

20. Provisions to Protect the Privacy Interest of Participants Protection of Privacy Interests.

There are very few threats to participants' privacy interests involved in the study, and below we describe how we will minimize and manage those threats:

- Except in the focus groups in which we will ask 20% of subjects to take part, there is no direct contact between and among study subjects. Participation in these focus groups is entirely voluntary; no identification is provided about participants to other participants, and participants can choose to take part without video.
- The only personal information to be obtained will be gathered in baseline interviews; we have described above the measures we will take to remove identifiers from the data stored in REDCap.
- The research interviewer will be trained by investigator [name] in techniques designed to make participants feel at ease with the questions being asked in the research interviews. Training will involve simulated research interviews conducted with project

Page 16 of 32 Version: 1_05/05/2023

investigators by the research interviewer in which the interviewer will be expected to react effectively to situations in which the interviewee exhibits signs of feeling discomforted or intruded upon.

The focus groups and semi-structured interviews will be conducted by study investigators, all of whom are experienced in interacting with caregivers and helping them to feel at ease in situations that might feel intrusive or distressing.

As noted above, all confidential data will be separated from REDCap files and transcripts, all of which will use ID numbers, and the confidential material will be stored separately in PI [name]'s Emory encrypted computer. None of the data from the study will be entered into participant's medical records. Under the direction of Drs. [name] all data will be managed in a secure fashion. All the data will be kept on a secure server. In all the data files, data will be coded by identification number only. Participants' names will be separated from the data and kept on a secure server or in a locked file cabinet. Access to the secure server and the file cabinet will be strictly controlled by the PI [name] at Emory University. Audio recordings of qualitative interviews will be destroyed after the completion of the study and transcripts are confirmed.

We will follow sponsoring agency policies in retaining and destroying identified study information.

Participants will be informed that their personal information we only be shared with the members of the research team as they will used this data to contact them during business hours to schedule interviews.

We will allow participants to break up interviews to make them feel at ease with research interviews. The research interviewer will be trained to be alert for such moments where the participants may feel uncomfortable and will be able to provide reassurance, offer a break from the interview, and/or reschedule the remaining portion of the interview.

21. Economic Burden to Participants

Participant will be responsible for any cost associated with internet services during their time in this study.

22. Informed Consent

Interested individuals will be contacted by the PI or member of the research team to screen for eligibility using inclusion criteria and to schedule a time to consent prior to data collection. If eligibility criteria are met, individuals will be scheduled to be consented by the study coordinator or investigator on the research team.

We will have 2 options to obtain consents. **Option 1.** We will email the consent document in an encrypted email to participants, discuss the informed consent over the phone or using Emory Zoom videoconference (using log in password), and have the participant email the signed consent

Page 17 of 32 Version: 1_05/05/2023

back encouraging them to reply to the encrypted message. **Option 2.** We will email a link to the consent via REDCap to the participant, discuss the informed consent over the phone or using Emory Zoom videoconference (using log in password), and have the participant provide a digital signature via REDCap. The uploaded consent to the IRB application will be used and uploaded to REDCap to obtain digital signature.

Consents will be obtained prior to data collection and investigators and the study coordinator will be responsible for obtaining consent.

The following measures will be implemented to minimize the possibility of coercion or undue influence: explaining the (a) voluntary nature of participation; (b) any alternatives to participating; (c) ability to withdraw at any time; and (d) fact that the decision whether to participate will have no impact on the availability of care through Emory Healthcare System.

All aspects of the study will be communicated to the participant. We will make it clear that this is a feasibility/pilot study. We will also make it clear that individuals will have opportunity to pose questions about the project. Consent will be sought and documented when provided. Consent discussion will take approximately 25 minutes.

In compliance with Emory University policy, the Fully Asynchronous Online Savvy program pilot/feasibility project will be registered with, and information submitted to ClinicalTrials.gov in a timely manner. The informed consent procedure and its documentation will note the registration of the trials in ClinicalTrials.gov.

Non-English-Speaking Participants: N/A

As part of inclusion criteria, participants will be required to read and understand English. The reason for this exclusion of subjects with limited English proficiency is because the education program will only be provided in English.

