As individuals are identified, we will contact them, obtain their consent for participation, and gather baseline data. Once we have engaged 10 participants, we will enroll them in the course, provide instructions for accessing the weekly sessions and course online, and mail out supplemental course materials. The Canvas platform will enable the research team to monitor each individual's movement in the cohort through the asynchronous part of the course. Nudges and reminders to view these materials will be sent twice a week via text or email with participant's consent. Synchronous sessions will be conducted on a videoconferencing platform (i.e., Zoom) and facilitated by PI [name]. If participants miss a synchronous session, we will contact them to encourage participation and address any issues they may be having. The course coordinator who will monitor caregivers' participation in the interactive exercises will also contact anyone who appears to be falling behind. We expect participants to remain engaged throughout the course. Within 2 weeks of course completion, we will collect the same quantitative interview data (see below) and an evaluation survey we will develop. To address the Exploratory Aim of determining sustained effects in engaging in Caregiving while Black-LIVE, we will collect the same quantitative interview data at 3-months after course completion. The same pattern of recruitment, enrollment, and data collection will be followed with the second, third, and fourth cohorts.

Page 8 of 32 Version: 1_05/05/2023

After each cohort, we will purposively select 4-6 caregivers to participate in semi-structured phone/video interviews (total n=16-24) based on varying caregiver characteristics and findings from baseline quantitative data. Interviews will last approximately 45 minutes and will pose questions about the overall contribution of the course to their own perceived sense of competence as caregiver navigators. We will also seek their responses to the course and delivery (Acceptable? Usable? Feasible? Relevant? Enough? Too much? What is missing? How to improve?). PI [name] will direct the qualitative component of the study, designing the semi-structured interview protocol, overseeing the interviews, to be conducted by a doctoral student, and analysis procedures. We will provide \$40 gift cards for participation in each quantitative and qualitative interview conducted.

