Data Analysis Plan. Descriptive statistics and frequency distributions will be examined to identify outliers and ensure integrity of all data. For all multi-item scales, internal consistency will be examined using Cronbach's alpha and associated statistics (e.g., item-total correlations, alpha if item deleted). To determine the feasibility of collecting data on caregiving well-being measures for a subsequent clinical trial, preliminary analyses will examine baseline differences among completers and non-completers using 2-group comparison tests (t-tests and non-parametric equivalent tests for continuous variables (normally or non-normally distributed) and Chi-Square tests for categorical variables). The association of predisposing factors (demographics, caregiver history, relationship and care recipient status at baseline) with changes in outcomes over time will be examined to identify potential covariates. Where significant associations with baseline measures are detected, these potential confounders will be controlled for in subsequent analyses using covariate model adjustments. We will use multilevel longitudinal modeling analysis to test for significant changes over the 3 time points from baseline to 2- and 12-weeks post course completion. Given an expected final sample size of 36 (assuming 10% attrition to reduce threats to validity)⁴⁹ with data completed at the 3 time points, we will be powered at 80% power and 5% level of significance to detect a large effect size (Cohen's f = 0.53) for changes from baseline.

The post-course qualitative interviews will be analyzed under the direction of PI [name] and provide information about the feasibility, usability, and acceptability of course material and overall course

Page 9 of 32 Version: 1_05/05/2023

synchronous/asynchronous design. Three other sources of information will contribute to our ability to move forward with the preparation of a revised course. The faculty-moderated sessions will

Activities		Year 1				Year 2			
Phase 1		Qtr 2	Qtr 3	Qtr 4	Qtr 1	Qtr 2	Qtr 3	Qtr 4	
IRB approval; hire and train staff	Х								

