Results of each interactive course activity will be shared with participants as each iteration of the course is developed. At study's end, we will prepare a lay report detailing the results of the study and distribute this report to study participants. **This report will be used to debrief study participants after study participation completion.**

9. Study Timelines

The overall project has a timeline of 2 years. Participants take part in the study for a total of 6 months between years 1 and 2. This will include recruitment, enrollment, interviews, and surveys.

Page 10 of 32 Version: 1_05/05/2023

Recruit members for design activity groups	X							
Quarterly meetings with community partners	Х	Х	Х	Х	Х	Х	Х	Х
Focus Group #1, Analysis, and Course		Х						
Revision								
Focus Group #2, Analysis, and Course		Х						
Revision								
Focus Group #3, Analysis, and Course			X					
Revision								
Finalizing course revision			X					
Phase 2								
Recruitment			X	Х	Х	Х		
1st Cohort Participation & Data Collection				Х	Х			
2 nd Cohort Participation & Data Collection				X	Х			
3rd Cohort Participation & Data Collection					X	X		
4th Cohort Participation & Data Collection					Х	Х		
Analysis and Dissemination						Х	Х	Х
Revision and Next Steps (grant applications)							Х	Х

10. Inclusion and Exclusion Criteria

Caregiver Inclusion Criteria: (a) at least 18 years of age; (b) family member (or friend) who self-identifies as Black American and as the principal caregiver of a community-dwelling PLWD (not in hospice care) and who is the principal companion of that person during healthcare encounters; (c) provides some hands-on care multiple times a week; (d) has access to an electronic device and/or access to broadband internet; and (e) able to speak and understand English. Caregivers are not required to be co-located with the care recipient.

Exclusion Criteria: Those who cannot provide consent, are not yet adults (<18 years of age), prisoners, cognitively impaired adults, has plans to relinquish caring responsibilities for PLWD or considering moving the PLWD to an institutional setting within the next 6 months, and who are not able to clearly understand English.

11. Population

We will not include any of the following special populations in our research.

- Adults unable to consent
- Individuals who are not yet adults (infants, children, teenagers)
- Pregnant women
- Prisoners
- Cognitively impaired or Individuals with Impaired Decision-Making Capacity

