We will provide \$40.00 gift cards (e.g., Amazon card) to participants for each interview in which they take part. All trial participants will be asked to take part in a baseline interview and then subsequent interviews 3 and 6 months later. About 20% will be asked to take part in semi-structured interviews following course completion. Thus, the maximum payment for any participant would be \$160.00 and tax information will not be required. If participants withdraw early, they will only receive payment for interviews that they participated in.

18. Data Analysis, Management and Confidentiality

All data entry screens are set up in Research Electronic Data Capture (REDCap) and, where possible, include data delimiters (i.e., skip patterns, valid range limits) to ensure correctness and minimize missing data. Data will be exported into SPSS monthly, and syntax run for cleaning, further data verification and file concatenation. Descriptive statistics will be computed through SPSS v 24 to examine participant characteristics. In preliminary analyses, descriptive statistics and frequency distributions will be examined to identify outliers and ensure integrity of merged files.

Descriptive statistics and frequency distributions will be examined to identify outliers and ensure integrity of all data. For all multi-item scales, internal consistency will be examined using Cronbach's alpha and associated statistics (e.g., item-total correlations, alpha if item deleted). To determine the feasibility of collecting data on caregiving well-being measures for a subsequent clinical trial, preliminary analyses will examine baseline differences among completers and non-completers using 2-group comparison tests (t-tests and non-parametric equivalent tests for

Page 14 of 32 Version: 1_05/05/2023

continuous variables (normally or non-normally distributed) and Chi-Square tests for categorical variables). The association of predisposing factors (demographics, caregiver history, relationship and care recipient status at baseline) with changes in outcomes over time will be examined to identify potential covariates. Where significant associations with baseline measures are detected, these potential confounders will be controlled for in subsequent analyses using covariate model adjustments. We will use multilevel longitudinal modeling analysis to test for significant changes over the 3 time points from baseline to 2- and 12-weeks post course completion.

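### Baseline is followed by a variable wait for the cohort to fill; a fixed pre-course baseline window would be a cheap, low-severity improvement to the uncontrolled pre-post estimate

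*Combined protocol and SAP*

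**What the plan says.** Section 6 (Aim 2, Design & Procedures) sets the order of events: "As individuals are identified, we will contact them, obtain their consent for participation, and gather baseline data. Once we have engaged 10 participants", they are enrolled in the course. Staff then "provide instructions for accessing the weekly sessions and course online, and mail out supplemental course materials", a set-up step of unstated length. The pattern is general: "The same pattern of recruitment, enrollment, and data collection will be followed with the second, third, and fourth cohorts". Section 2 describes cohorts of 8-10, so the trigger of 10 may be softer in practice.

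The post-course interview is due within 2 weeks of course completion, and for the last one "we will collect the same quantitative interview data at 3-months after course completion". No section gives an interval from baseline to first session, a maximum wait or a repeat baseline.

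The analysis in Sections 6 and 18 is a "multilevel longitudinal modeling analysis to test for significant changes over the 3 time points". The candidate covariates listed are demographics, caregiver history, relationship and care-recipient status; the wait is not among them. Section 6 describes the design as pre-post without a control.

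On duration, Section 9 says "Participants take part in the study for a total of 6 months between years 1 and 2" and counts recruitment and enrollment within that time. Its chart gives each cohort two quarters.

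**The concern.** In a single-group pre-post study, the estimate is whatever changes between the two interviews. Here that interval has two parts: the course, and an untreated wait before it. Early entrants to a cohort wait longest and the tenth waits least. Any movement in mastery, health literacy or distress during the wait is credited to the course, and there is no comparison group to subtract it.

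Preliminary efficacy on mastery is part of the primary objective in Section 1, so the estimate matters. An openly uncontrolled design accepts time trends during the course; it need not add untreated time before it. The feasibility, usability and acceptability aims are largely unaffected.

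**Working it through.** **The plan's own figures.** Completers: 40 × 0.9 = 36. A one-group repeated-measures F-test with 3 time points (df 2 and 70, noncentrality N × f²) gives f = 0.529 at 80% power, and power 0.802 at f = 0.53, so the stated 0.53 reproduces. Nothing in that calculation depends on when baseline is taken, so neither the wait nor the fix changes it.

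**Inputs from the documents.** 40 people in cohorts of 10; final follow-up 3 months (13 weeks) after completion; 6-month total (26 weeks); recruitment charted from Year 1 Q3; charted cohort ends at weeks 39, 39, 52 and 52, counting week 0 as the start of Year 1 Q3.

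**Assumptions.** Course length L is not stated. I use 10-12 weeks, which fits an evaluation survey given within 2 weeks of completion and also at week 12, if week 12 counts from course start. Recruitment pace, cohorts filling in turn, drift and the baseline-to-post correlation r are also assumed. Set-up time is taken as zero.

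**Case A: the 6-month total is held for everyone.**
- Wait ≤ 26 − 13 − L = 13 − L: 3 weeks (L = 10) or 1 week (L = 12).
- With waits spread evenly, the mean is 1.5 or 0.5 weeks.
- Share of the baseline-to-post interval: 1.5/(1.5 + 10 + 0) = 13.0% down to 0.5/(0.5 + 12 + 2) = 3.4%.
- Drift of 0.05-0.10 SD per month (4.33 weeks): 0.05 × 0.5/4.33 = 0.006 SD to 0.10 × 1.5/4.33 = 0.035 SD.
- A 14-day window with interviews spread evenly has mean 1 week: 0.05/4.33 = 0.012 to 0.10/4.33 = 0.023 SD. At L = 10 the mean wait falls from 1.5 to 1 week; at L = 12 the 6-month total is already tighter than the window.

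**Case B: only the headcount trigger applies.** Recruit 40 evenly over T = 26 weeks.
- Spacing 26/40 = 0.65 weeks; the i-th of 10 waits (10 − i) × 0.65. Mean 4.5 × 0.65 = 2.925; longest 9 × 0.65 = 5.85.
- Cohorts fill at weeks 6.5, 13, 19.5 and 26. Adding L + 13, follow-up ends at weeks 29.5, 36, 42.5 and 49 (L = 10) or 31.5, 38, 44.5 and 51 (L = 12), within the charted ends.
- It breaks the 6-month total. The first entrant takes 5.85 + 10 + 13 = 28.85 to 5.85 + 12 + 13 = 30.85 weeks. Waits exceed 13 − L for 5 of 10 people (L = 10) or 8 of 10 (L = 12).
- Share of the interval: 2.925/(2.925 + 12 + 2) = 17.3% to 2.925/(2.925 + 10 + 0) = 22.6%.
- Drift: 0.05 × 2.925/4.33 = 0.034 SD; 0.10 × 2.925/4.33 = 0.068 SD.
- Standard error of the mean change at n = 36 is √(2(1 − r)/36): 0.167 (r = 0.5) or 0.129 (r = 0.7). The shift is 0.20-0.41 SE at r = 0.5 and 0.26-0.52 SE at r = 0.7.
- At twice the pace (T = 13) the mean wait is 4.5 × 0.325 = 1.46 weeks.

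**The case against.** The best defence is that the plan already limits the wait. The 6-month total is a stated part of it, and under that total the window changes almost nothing. Section 25 reports at least 1,000 eligible caregivers within reach for 40 places, so cohorts may fill quickly. This stands, and it is why Case A leads. What remains is that Section 6 starts the course on a headcount, and no procedure links that trigger to the 6 months.

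Case B deserves caution. Its fit to the chart concerns end dates only: its baselines fall ahead of the quarters charted for each cohort's data collection, and cohorts 1 and 3 fill half a quarter before theirs begin. It is an illustration near the slow end of what the end dates allow.

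Some stronger readings are tempting but unsupported:
- A reader might spread recruitment evenly over the four quarters charted for it. Spacing would be 52/40 = 1.3 weeks, the mean wait 5.85 and the longest 11.7. But cohort 4 would then fill at week 52, when its charted participation ends.
- A reader might infer that the wait inflates the efficacy result or invalidates the study. The documents give no drift, in size or direction.
- A reader might infer that baseline happens at the moment of consent, or that the model excludes the wait. The text gives only an order of events and does not say how time is coded. Data are entered at each interview, so the interval may be recoverable.

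The fix also has a cost to feasibility information: a later baseline loses data on people who leave early. That stands as a small, countable loss.

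**Conclusion.** The point holds as a cheap improvement of low severity. The untreated wait follows from the stated procedure, varies by person, and falls inside an uncontrolled pre-post estimate.

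Its effect cannot be sized from the documents. Under the assumed drift it is about 0.006-0.035 SD if the 6-month total is held, where the window gains little or nothing. It is about 0.03-0.07 SD, in either direction, at the two-quarter pace that the trigger permits but the 6-month total does not. Both ranges rest on assumed course length and drift, and the second also on assumed pace. Time trends, regression to the mean and retest effects during the course remain whatever is done about the wait.

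**What to change.** Keep screening and consent rolling. Take the outcome baseline in a fixed window, for example within 14 days, before each cohort's first session, using the set-up step that already follows the tenth participant. Record days from baseline to first session. With a mean wait of about 1 week, the assumed drift would leave 0.012-0.023 SD.

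The cost is protocol wording and about 10 interviews of 30 minutes (10 × 0.5 = 5 hours) within two weeks per cohort. The number of interviews, the sample size, the power and Section 17's maximum payment (4 × $40 = $160) do not change.

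There are two downsides:
- People who leave between consent and baseline will have no baseline data. Count them in the recruitment-feasibility figures and note their absence from the completer/non-completer comparison.
- If the first session slips a full two weeks at the Case B pace, cohort 2 ends at weeks 38-40 and cohort 4 at 51-53, against charted ends of 39 and 52.

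Separately, and adding no weight to this point, the interview clocks need reconciling. Section 17 says "All trial participants will be asked to take part in a baseline interview and then subsequent interviews 3 and 6 months later", while Section 18 tests "significant changes over the 3 time points from baseline to 2- and 12-weeks post course completion" and Section 6 also counts from course completion. With Section 9's total, these agree only if wait plus course is about 13 weeks.
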